STUDY PROTOCOL

1. Study Title

Levetiracetam Versus Phenobarbitone for the Treatment of Neonatal Seizures in a Tertiary Care Hospital

Short title/acronyms: Levetiracetam Versus Phenobarbitone for the Treatment of Neonatal Seizures

2. Protocol ID

DHQ-DIK-IWEB NO. 4806

Date: 26 February 2024.

ClinicalTrials.gov Identifier: NCT Not Yet Assigned

3. Background & Rationale

Neonatal seizures are the most common neurological emergency in neonates and are associated with significant morbidity and mortality. Phenobarbitone has traditionally been the first-line anticonvulsant; however, its efficacy is limited and it has significant adverse effects. Levetiracetam is emerging as a safer alternative with promising seizure control rates. This study aims to compare the efficacy and safety of levetiracetam versus phenobarbitone in neonates with seizures.

4. Objectives

Primary Objective

To compare seizure control rates within 24 hours between levetiracetam and phenobarbitone in neonates with clinically diagnosed seizures.

Secondary Objectives

- To compare time to seizure cessation between both drugs.
- To compare the need for second-line anticonvulsant therapy.
- To compare seizure recurrence during hospital stay.
- To compare adverse drug reactions.
- To compare mortality rates.

5. Study Design

A prospective randomized controlled trial conducted at the Neonatal Intensive Care Unit (NICU) and Pediatric wards of a tertiary care hospital.

6. Study Setting

Neonatal Intensive Care Unit (NICU) and Pediatric ward at [Your Hospital Name], Pakistan.

7. Study Population

Neonates (0–28 days) with clinically diagnosed seizures admitted to NICU or Pediatric ward.

8. Sample Size

Based on previous literature, assuming seizure control rates of 70% with levetiracetam and 50% with phenobarbitone, with 80% power and 5% significance level, the calculated sample size is **n = 100 (50 in each group)**. However we will include all the patients accepting the inclusion criteria during one year of study.

9. Inclusion Criteria

- Neonates (0–28 days old) with clinically diagnosed seizures.
- Term and preterm neonates.
- Parents/legal guardians provide informed consent.

10. Exclusion Criteria

- Major congenital anomalies or genetic syndromes.
- Severe renal or hepatic impairment.
- Neonates already receiving anticonvulsants before admission.
- Neonates with metabolic seizures not responding after correction.
- Neonates with CNS infection requiring specific treatment (unless seizures persist).
- Parents refuse consent.

11. Intervention

Arm A: Levetiracetam

- Loading dose: 20 mg/kg IV
- Repeat dose: 20 mg/kg IV after 12 hours if seizures persist
- Maintenance dose: 10 mg/kg IV/PO twice daily until seizure control or discharge

Arm B: Phenobarbitone

- Loading dose: 20 mg/kg IV
- Repeat dose: 10 mg/kg IV after 20 minutes if seizures persist
- Maintenance dose: 5 mg/kg IV/PO once daily until seizure control or discharge

12. Outcome Measures

Primary Outcome

Seizure control rate within 24 hours after first-line treatment.

Secondary Outcomes

- Time to seizure cessation
- Need for second-line anticonvulsant
- Seizure recurrence during hospital stays
- Adverse drug reactions
- Mortality during hospital stay

13. Study Procedures

1. Neonates with clinical seizures will be assessed by pediatric/neonatology team.
2. Eligible neonates will be randomized into either levetiracetam or phenobarbitone group.
3. Baseline data including demographic details, gestational age, birth weight, and clinical status will be recorded.
4. Standard investigations will be done (CBC, blood glucose, electrolytes, ABG, neuroimaging if required).
5. Treatment will be administered as per group allocation.
6. Monitoring of seizure activity and side effects will be done for 72 hours and until discharge.
7. Data will be recorded on a structured proforma.

14. Randomization

Simple randomization using Lottery method.

15. Data Collection

Data will be collected on a structured proforma and entered into SPSS version 25.

16. Ethical Considerations

Approval will be obtained from the Institutional Review Board (IRB). Informed consent will be obtained from parents/legal guardians.

17. Principal Investigator:

[name]

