STATISTICAL ANALYSIS PLAN (SAP)

Study: Levetiracetam Versus Phenobarbitone for the Treatment of Neonatal Seizures in a
Tertiary Care Hospital

Principal Investigator: [name]

Official Study Title:

**Levetiracetam Versus Phenobarbitone for the Treatment of Neonatal Seizures in a
Tertiary Care Hospital**

Short title/acronyms: **Levetiracetam Versus Phenobarbitone for the Treatment of Neonatal
Seizures**

ClinicalTrials.gov Identifier:

NCT Not Yet Assigned

Organization's Unique Protocol ID:

DHQ-DIK-IREB NO. 4806

Document Type:

Statistical Analysis Plan (SAP)

Date:

Study Start Date

April 08 2024

Primary Completion Date

March 31 2025

Study Completion Date

April 10 2025

Prepared By:

[name]

Analysis Population

- **All randomized neonates** (Intention-to-Treat, ITT)
- **Per-protocol population** for sensitivity analysis (neonates who completed treatment as per protocol)

Descriptive Statistics

- **Continuous variables:** mean \pm SD or median (IQR)
- **Categorical variables:** frequency (%)

Outcome Analysis

Primary Outcome:

- Seizure control rate within 24 hours
 - **Compare** seizure control between levetiracetam and phenobarbitone groups
 - **Statistical Test:** Chi-square or Fisher's exact test
 - **Significance level:** $\alpha = 0.05$

Secondary Outcome Analysis

- **Time to seizure cessation**
 - Independent t-test or Mann–Whitney U test
- **Need for second-line anticonvulsant**
 - Chi-square test
- **Seizure recurrence during hospital stay**
 - Chi-square test
- **Adverse drug reactions**
 - Chi-square test
- **Mortality during hospital stay**
 - Chi-square test

Subgroup Analysis (optional)

- Preterm vs Term neonates
- Birth weight <2500 g vs ≥ 2500 g
- Etiology of seizures (HIE vs metabolic vs infection vs others)

Handling Missing Data

- **Multiple imputation** if missing data $> 5\%$
- **Sensitivity analysis** comparing complete case vs imputed dataset

Software

- Analysis performed using **SPSS version 23**,

Reporting

- **Two-sided p-values**
- **95% confidence intervals** for effect estimates
- **Tables and figures** for primary and secondary outcomes

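### The stated 100 neonates (50 per group) give about 53% power for 70% versus 50%, not 80%; 93 per group (186 in total) are needed.

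*Protocol*

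**What the plan says.** Protocol Section 8 (Sample Size) gives its inputs as "assuming seizure control rates of 70% with levetiracetam and 50% with phenobarbitone, with 80% power and 5% significance level" and concludes that "the calculated sample size is n = 100 (50 in each group"). It then adds an open recruitment rule: "However we will include all the patients accepting the inclusion criteria during one year of study".

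Section 8 does not say whether the test is one- or two-sided. The SAP does: under Reporting it specifies "Two-sided p-values", and under Outcome Analysis it sets α = 0.05 for the primary outcome, tested by chi-square or Fisher's exact test. The SAP has no sample size section, so Section 8 is the only justification of trial size in either document.

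**The concern.** Section 8 supplies everything a two-proportion calculation needs, and 50 per group is far too few for 70% versus 50% at 80% power. A reader who trusts the section will believe the trial can reliably detect a 20-point difference in seizure control at 100 neonates.

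If enrolment ends near 100 and the levetiracetam advantage really is 20 points, the trial has roughly an even chance of missing it. A non-significant result could then be set against a documented power of 80% and taken as evidence that the drugs perform alike, which a trial of that size could not support.

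**Working it through.** **Inputs.** p₁ = 0.70, p₂ = 0.50, power 0.80 and α = 0.05 (protocol Section 8); two-sided testing (SAP, Reporting); equal groups (protocol Section 8). Difference d = 0.20, mean rate p̄ = 0.60. Normal quantiles: 1.96 (two-sided 5%), 1.645 (one-sided 5%), 0.8416 (80% power). No allowance for dropout is made, because the documents state none.

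**Trying to reproduce 50 per group.** The pooled formula, which matches the uncorrected chi-square test, is

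n = [z_α √(2p̄(1−p̄)) + z_β √(p₁(1−p₁) + p₂(1−p₂))]² / d²

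- z_α term: 1.96 × √0.48 = 1.358
- z_β term: 0.8416 × √(0.21 + 0.25) = 0.571
- n = (1.358 + 0.571)² / 0.04 = 93.0, so **93 per group, 186 in total**

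The other standard versions, per group:

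| Method | Two-sided 5% | One-sided 5% |
|---|---|---|
| Unpooled variance | 91 | 72 |
| Pooled variance | 93 | 74 |
| Arcsine | 93 | 74 |
| Continuity-corrected | 103 | 83 |

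None gives 50. The only calculation that comes near is a one-sample test of 70% against a fixed 50%, (1.96 × √0.25 + 0.8416 × √0.21)² / 0.04 = 46.6, so 47. That does not fit a two-group trial, and the protocol does not say it was used.

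**Power at 50 per group.** By the pooled formula,

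power = Φ[(d√n − 1.96 √0.48) / √0.46] = Φ[(1.414 − 1.358) / 0.678] = Φ(0.083) = **53.3%**

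Exact enumeration of all outcomes with 50 per group gives 54.6% for the uncorrected (Pearson) chi-square test and 46.3% for Fisher's exact test. A one-sided 5% test would have 65.7% by the pooled formula.

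**Power at other sizes** (same formula, two-sided):

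| Per group | Total | Power |
|---|---|---|
| 50 | 100 | 53% |
| 60 | 120 | 61% |
| 75 | 150 | 71% |
| 93 | 186 | 80% |
| 100 | 200 | 83% |

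**Which test goes with 93.** Exact power at 93 per group is 79.9% for the uncorrected chi-square test but 75.1% for Fisher's. At 103 per group, Fisher's reaches 81.1%.

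**What 50 per group can do.** Against 50%, 80% power is reached at about 77%: a rate of 76% gives 77.7% power and 77% gives 81.0%. The detectable difference is therefore about 27 points. If the observed rates were 70% and 50%, the 95% interval would be 20 ± 1.96 × √(0.46/50) = 20 ± 19 points, or about 1 to 39.

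**Shortfall.** (186 − 100) / 186 = 46%.

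**The case against.** The best reply is that enrolment is not capped at 100. Section 8 goes on to include every eligible neonate for one year, and the SAP dates (start 8 April 2024, primary completion 31 March 2025) fit a sample set by the calendar. Realised power is therefore unknown: it would be about 71% at 150 neonates and above 80% at 200. This stands as far as it goes, and 53% should be quoted as the power at 100, not as the power of the trial. It does not rescue the calculation. The one-year rule carries no minimum and no expected number, and it treats 100 as already sufficient. A team that reached 120 would think it had passed its target while holding 61% power.

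Three smaller points also have force:

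- The SAP already promises 95% confidence intervals for effect estimates. Only the instruction to interpret a null result through them is new.
- The figure of 93 belongs to the uncorrected chi-square test, and the SAP also allows Fisher's test without a rule for choosing. Any replacement figure should name its test.
- The error does not bias the estimate or invalidate the test. It misstates what the trial was planned to detect.

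The documents do not show how the error arose. The stated total of 100 lies within the two-sided per-group results of 91 to 103, so a per-group figure may have been used as the total. That is conjecture, and nothing here depends on it.

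**Conclusion.** The concern holds. The size and power stated in Section 8 are inconsistent with each other, by a factor of nearly two in sample size (186 ÷ 100 = 1.86). The conclusion rests on the protocol's own rates, equal groups and the SAP's two-sided 5% level. It is not sensitive to the choice of formula, since two-sided results run from 91 to 103 per group, or to sidedness, since the most lenient one-sided version still needs 72. What the documents cannot settle is the trial's actual power, which depends on how many neonates were enrolled. Because this is the sole justification of trial size and it supports the primary objective, it must be corrected.

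**What to change.** Replace the figure in Section 8 with text such as:

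> *For control rates of 70% and 50%, a two-sided 5% uncorrected chi-square test has 80% power with 93 neonates per group (186 in total). With 50 per group, power is about 53%, and the difference detectable with 80% power is about 27 percentage points. Recruitment is limited to one year; power will be restated for the number randomised.*

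If Fisher's exact test is to be the primary test, quote 103 per group (206 in total) instead and give its power at 50 per group as 46%.

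In the report, state power at the number actually randomised, using the planned 70% and 50% and not the observed rates. Withdraw the 80% claim if fewer than 186 were enrolled (206 under Fisher's test). Interpret a non-significant primary result through the 95% confidence interval for the difference, saying which differences it does and does not exclude.

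The cost is wording only. The stated power becomes less favourable, and correcting the figure requires no additional patients and no change to treatment or data collection.

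### As worded, the metabolic exclusion removes neonates whose seizures persist after correction and leaves eligible those whose seizures stop with correction alone; it looks reversed

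*Protocol*

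**What the plan says.** Protocol Section 9 admits term and preterm neonates with clinically diagnosed seizures and consent. It does not require that seizures persist after a metabolic abnormality has been treated.

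Section 10 lists among the exclusions "Neonates with metabolic seizures not responding after correction". The next bullet reads "Neonates with CNS infection requiring specific treatment (unless seizures persist", so a neonate with CNS infection comes in when seizures continue.

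Section 13 begins with "Neonates with clinical seizures will be assessed by pediatric/neonatology team" (step 1), then "Eligible neonates will be randomized into either levetiracetam or phenobarbitone group" (step 2). Glucose and electrolytes appear at step 4: "Standard investigations will be done (CBC, blood glucose, electrolytes, ABG, neuroimaging if required". No step describes metabolic correction.

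The primary outcome in Section 12 is "Seizure control rate within 24 hours after first-line treatment", with no rule for a neonate who is corrected at about the same time as the study drug is given. Section 8 fixes the recruitment period rather than the number: "However we will include all the patients accepting the inclusion criteria during one year of study".

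The SAP analyses all randomised neonates as ITT. Its optional subgroups include "Etiology of seizures (HIE vs metabolic vs infection vs others", without definitions or cut-offs.

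**The concern.** The trial asks which anticonvulsant controls seizures better. A neonate whose seizures stop with glucose or electrolyte correction says little about that, while a neonate who still seizes after correction is a natural candidate for the comparison. The exclusion as worded does the reverse on both counts.

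Two things are at stake. Correction-responders who are enrolled would probably be recorded as controlled whichever drug they were given, which pulls the two arms together. They may also receive an anticonvulsant that they do not need. In addition, a reader of the results could not tell from the plan which metabolic neonates the trial population contains.

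**Working it through.** **The text, side by side**

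| Neonate | Metabolic rule as written | CNS-infection rule as written |
|---|---|---|
| Seizures persist after the cause is treated | excluded | eligible |
| Seizures stop when the cause is treated | eligible (no criterion excludes) | excluded |

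Excluding persistent metabolic seizures could be deliberate. The second row of the metabolic column is the same under that reading, so the gap for correction-responders does not depend on intent.

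**The plan's own figure.** Section 8 gives 50 per arm for 70% versus 50%, 80% power and 5% significance. The SAP specifies two-sided p-values. With pooled variance, two-sided alpha 0.05:

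power = Φ{ [d√n − 1.96√(2p̄(1−p̄))] / √(p₁(1−p₁) + p₂(1−p₂)) }

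At n = 50, d = 0.20 and p̄ = 0.60 this is Φ{(1.414 − 1.358)/0.678} = 53.3%. The same method needs 93 per arm for 80% power, so the stated size is not reproduced. That is a separate matter. It is used here only as the starting level of power.

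**Effect on the difference.** Let m be the responders' share of enrolment, the same in both arms on average under randomisation, and c their control rate, assumed equal in both arms. Each arm's rate is mc + (1−m)p. The term mc cancels, so the difference is (1−m)(0.70 − 0.50), whatever c is:

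- m = 5%: 0.95 × 20 = 19 points
- m = 10%: 0.90 × 20 = 18 points
- m = 20%: 0.80 × 20 = 16 points

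**Effect on power.** The documents do not give m; the values are assumptions. The year's intake is assumed to be 50 per arm. Because Section 8 recruits for a fixed year, excluded neonates are not replaced, and 50(1−m) per arm remain. Persistent metabolic cases that a reworded rule would admit are ignored.

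Case 1: 70%/50% hold in the other neonates, and responders are controlled 100% of the time.

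| m | Rates with responders | Power, n = 50 | n per arm without | Power without | Gain (points) |
|---|---|---|---|---|---|
| 2% | 70.6 / 51.0% | 51.9% | 49 | 52.5% | about 0.5 |
| 5% | 71.5 / 52.5% | 49.9% | 47.5 | 51.2% | 1.3 |
| 10% | 73.0 / 55.0% | 46.6% | 45 | 49.0% | 2.5 |
| 20% | 76.0 / 60.0% | 40.2% | 40 | 44.5% | 4.4 |

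Case 2: 70%/50% already include responders, so the rates without them are (p−m)/(1−m). Power with responders is 53.3% throughout.

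| m | Rates without responders | n per arm without | Power without | Gain (points) |
|---|---|---|---|---|
| 2% | 69.4 / 49.0% | 49 | 53.9% | about 0.5 |
| 5% | 68.4 / 47.4% | 47.5 | 54.8% | 1.5 |
| 10% | 66.7 / 44.4% | 45 | 56.6% | 3.3 |
| 20% | 62.5 / 37.5% | 40 | 61.2% | 7.9 |

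Gains are taken before rounding. If responders are controlled 90% of the time instead of 100%, the Case 1 differences at m = 5, 10 and 20% stay at 19, 18 and 16 points, and power with responders is 49.7, 46.1 and 39.2%.

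**The case against.** The intent is not stated. Leaving out seizures that resist metabolic correction is a coherent choice in a list that also excludes genetic syndromes and severe renal or hepatic impairment, and different causes may reasonably have different rules. A reader might infer that the bullet is certainly a drafting error. The documents show only that it conflicts with its neighbour and that no reason is given. This objection stands, but it does not make responders ineligible.

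Nothing says that responders would in fact be randomised. Judging non-response presupposes correction and reassessment, perhaps within step 1, and a neonate who has stopped seizing is not an obvious candidate for an intravenous load. This also stands as a limit: the text permits their enrolment but does not show that it happened.

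A reader might infer from steps 2 and 4 that glucose was first checked after the draw. Section 13 also puts baseline data after randomisation, at step 3, so the numbering may be a list of activities rather than a timeline. The step order is weak evidence, and the point does not rest on it.

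The SAP's etiology subgroup gives partial cover. It would let a reader see results by cause, but it is optional, undefined, and not a pooled non-metabolic analysis.

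**Conclusion.** The concern holds in a limited form. As written, the rule excludes persistent metabolic seizures and fails to exclude those that correction alone stops. That is a defect of wording under either reading of the intent.

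The consequence is dilution by the factor (1−m), with m unknown. It assumes equal control in responders of both arms. A reader might infer that the result is biased toward one drug or that the trial loses much of its power; neither is supported. The pull is toward no difference, and removing responders gains 0.5 to 4.4 power points in Case 1. The largest figure, 7.9 points, needs both m = 20% and planning rates that already include responders. The net change in numbers is also unknown, because rewording would admit some persistent cases.

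The main reasons for the change are to define the population clearly and to avoid needless dosing, not to gain power.

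**What to change.** **Protocol Section 10.** Reword the bullet to: *Metabolic seizures, unless seizures persist after correction*. If persistent cases are also to stay out, name both groups as excluded.

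**Protocol Section 13, step 1.** State that a rapid glucose check, correction where needed, and reassessment come before the draw.

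**SAP.** Keep every randomised neonate in the ITT set, including any found to be metabolic afterwards.

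**If enrolment has closed** (the SAP gives primary completion as March 31 2025), the rewording cannot change who entered. State which metabolic neonates were eligible in practice. Report the primary outcome in neonates without a correctable metabolic abnormality as one sensitivity analysis:

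- Classify both arms by fixed cut-offs on the first sample taken before any correction. The step 4 sample will not do if correction came earlier, because a corrected neonate could then look normal. Do not classify by whether seizures stopped.
- Say that it estimates the effect in non-metabolic neonates, drops any persistent metabolic cases as well, and does not replace the ITT result.
- Label it post hoc if outcomes have been seen.

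**Cost.** The wording changes are small. Glucose is already a listed investigation, but testing before the draw assumes a rapid bedside test, which the protocol does not mention. There is a short wait before randomisation, longer where correction is needed, and possibly a small change in the number eligible. The sensitivity analysis depends on a pre-correction result having been recorded.

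### Persisting seizures are re-dosed after 12 hours with levetiracetam but after 20 minutes with phenobarbitone, so time to cessation and second-line need compare retreatment schedules as well as drugs

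*Protocol*

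**What the plan says.** Protocol Section 11 starts both arms with a 20 mg/kg intravenous load. If seizures persist, Arm A (levetiracetam) has "Repeat dose: 20 mg/kg IV after 12 hours if seizures persist" and Arm B (phenobarbitone) has "Repeat dose: 10 mg/kg IV after 20 minutes if seizures persist". Arm A also has "Maintenance dose: 10 mg/kg IV/PO twice daily until seizure control or discharge", so some drug may be given between the load and the repeat.

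One secondary objective in Section 4 is "To compare time to seizure cessation between both drugs". Need for second-line therapy is another. Section 12 lists both as outcomes and limits neither to the period before a repeat dose. The SAP tests time to cessation with a t-test or Mann–Whitney and second-line need with chi-square, and neither analysis refers to re-dosing. Neither document says when, or on what criterion, a second drug is started. Section 13 says "Monitoring of seizure activity and side effects will be done for 72 hours and until discharge", with no observation frequency.

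**The concern.** A neonate still seizing half an hour after the load may already have had a second dose in Arm B, but is not due one for more than 11 hours in Arm A. Both outcomes run past the point where the schedules part.

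In Arm A, clinicians can wait, which lengthens time to cessation for anyone who needs the repeat. Or they can move to a second drug, in which case the neonate counts as needing second-line treatment after one load, whereas an Arm B neonate may have had two. Either way the arms can differ when the drugs do not. The objective is worded as a comparison of drugs, so the report would read such a difference as a drug effect.

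**Working it through.** **Inputs from the documents.** Repeat at 12 h (720 min) in Arm A and 20 min in Arm B. The gap is 720 − 20 = 700 min = 11.67 h, a 36-fold ratio. Trial size is 50 per arm (Section 8), used only for illustration because Section 8 adds "However we will include all the patients accepting the inclusion criteria during one year of study".

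**Assumptions, not in the documents.** The drugs are identical: 50% stop on the load, and a further share q stop only on the repeat, with q = 0.10, 0.20 or 0.30. Stops occur within 20 min of the effective dose, spread evenly, unless stated otherwise. Time to cessation is analysed among those who stop, because the SAP gives no rule for the rest. Significance figures for time to cessation come from several thousand simulated trials per setting and are good to a percentage point or two. The two cases below are alternatives, and real practice may mix them.

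**Case 1: clinicians wait for the 12-hour repeat.** The share of stoppers who needed the repeat is s = q/(0.50 + q) = 0.167, 0.286, 0.375.

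- Extra mean time in Arm A if nobody stops in between: s × 11.67 h = 1.94, 3.33, 4.38 h.
- If late responders instead stop evenly over the interval, for example on maintenance doses: half of that, 0.97, 1.67, 2.19 h.
- Wider inputs (40% to 70% stop on the load, 20% to 50% of the remainder on the repeat): with load response p and repeat response r, s = (1−p)r / [p + (1−p)r]. This runs from 0.06/0.76 to 0.30/0.70, so the delay runs from 0.9 to 5.0 h.
- Chance that a random Arm A time is later than a random Arm B time: 0.5 + 0.5s² = 0.514, 0.541, 0.570.

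The proportion of such trials significant at 5%, with nobody stopping in between, depends on the test and on how quickly first-load responders stop:

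| First-load stop times | Test | q = 0.10 | q = 0.20 | q = 0.30 |
|---|---|---|---|---|
| Even over 20 min | t-test | 69% | 99% | >99% |
| Even over 20 min | Mann–Whitney | 5% | 9% | 20% |
| Exponential, mean 1 h | t-test | 71% | 99% | >99% |
| Exponential, mean 1 h | Mann–Whitney | 26% | 67% | 91% |

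The t-test rows need three things together: clinicians wait, nobody stops in between, and a t-test is applied to two-peaked data. They are not a forecast.

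**Case 2: Arm A non-responders get a second drug before 12 h.** Let f be the fraction of them pre-empted. Second-line need is 0.50f + (1−f)(0.50−q) in Arm A and 0.50−q in Arm B, so the gap is f × q.

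| f | q | Arm A v Arm B | Chi-square p<0.05 (exact enumeration) |
|---|---|---|---|
| 1 | 0.10 | 50% v 40% | 18% |
| 1 | 0.20 | 50% v 30% | 55% |
| 1 | 0.30 | 50% v 20% | 89% |
| 0.5 | 0.10 | 45% v 40% | 9% |
| 0.5 | 0.20 | 40% v 30% | 18% |
| 0.5 | 0.30 | 35% v 20% | 39% |

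Time to cessation can now move the other way. With f = 1, and stops after a second drug not credited to the first, Arm A's stoppers are all first-load responders (mean 10 min), while Arm B's include repeat responders (mean 30 min). Arm A looks shorter by s × 20 min = 3.3, 5.7, 7.5 min. The t-test is significant in about 29%, 67%, 90% and Mann–Whitney in about 16%, 46%, 75%.

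Second-line need can also reverse. If clinicians wait and a share w of those who would fail both doses stop during the 12 hours, spontaneously or on maintenance, Arm A's need falls to (0.50−q)(1−w). Arm B stays at 0.50−q if its second drug follows soon after the 20-minute repeat.

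**24-hour control.** Both repeats fall within 24 h of the load. If clinicians wait and any stop within 24 h counts, both arms reach 0.50 + q and there is no shift.

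**The case against.** The strongest reply is that drug-specific schedules are part of the randomised interventions. Section 11 states both openly, and a trial may compare two regimens as used. That stands, and it is why no change of dose or timing is proposed. It does not rescue an objective worded as a comparison of the two drugs, or second-line counts that mix neonates who have had one load with neonates who have had two.

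A second reply is that the response shares are invented and the significance figures swing widely with them. That also stands. Mann–Whitney alone runs from 5% to 91%, and two-peaked data would ordinarily go to that test. The numbers show that a schedule effect can arise, not how large it will be.

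A reader might infer that the imbalance always works against levetiracetam and so would mask or reverse the benefit in Section 8 ("assuming seizure control rates of 70% with levetiracetam and 50% with phenobarbitone"). The documents do not support that. Either outcome can move in either direction, depending on a second-line trigger and a crediting rule that are not stated. Section 8's assumption also concerns control rates, not these two outcomes.

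**Conclusion.** The point holds for the two secondary outcomes. The 12-hour and 20-minute intervals are certain from the text, and nothing in either document offsets them. That a schedule effect could be reported as a drug effect follows from the intervals and the planned tests. Its direction and size are not established. They rest on assumed response shares and on whether clinicians wait: roughly 1 to 4.4 h longer cessation with levetiracetam if they do, and up to 10 to 30 points more second-line use with levetiracetam if they do not, with cessation then possibly a few minutes shorter.

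A reader might go further and conclude that the primary outcome, "Seizure control rate within 24 hours after first-line treatment", is invalidated. The documents do not support that either, since there is one plausible reading with no shift at all. How control is defined and when the 24-hour clock starts are gaps that would exist with equal intervals, and they belong to a separate point. This is a cheap improvement that should be made, not a fatal flaw.

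**What to change.** 1. In Protocol Section 4 and in the conclusions, describe the comparison as one of two regimens, including their retreatment schedules.
2. Record on the proforma the times of each first-line dose, of cessation and of any second-line start. In the SAP, report second-line need split by whether the repeat dose had been given, and report time to cessation with the numbers who stopped before and after the repeat.
3. Where times allow, add to Protocol Sections 12 and 13 and the SAP a supportive comparison of the proportion whose clinical seizures stopped within 20 minutes of the first load, before any repeat or second drug. State that it measures early response only and favours the faster-acting drug.

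Cost: a narrower claim, a few proforma fields, one extra table, and an added 20-minute bedside reading in Arm A, which has no decision point then. The SAP gives a primary completion date of March 31 2025. If enrolment has closed, items 2 and 3 apply only where times were recorded, but item 1 can still be done.

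### The safety outcome depends on judging that the drug caused the event, with no causality method or masking stated, so differential attribution could produce a safety difference where event rates are equal

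*Protocol*

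**What the plan says.** Protocol section 4 sets the objective "To compare adverse drug reactions". Section 12 lists the outcome by name only, "Adverse drug reactions", and the SAP assigns it a chi-square test under its secondary outcomes. Neither document adds a definition, an event list, a severity grade, a causality scale or a named assessor.

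On ascertainment, Protocol section 13, item 6, says "Monitoring of seizure activity and side effects will be done for 72 hours and until discharge". Sections 13 and 15 refer to a structured proforma, whose content is not given.

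On masking, the design statement in section 5 is "A prospective randomized controlled trial conducted at the Neonatal Intensive Care Unit (NICU) and Pediatric wards of a tertiary care hospital" and section 14 reads "Simple randomization using Lottery method". Neither mentions masking of staff, parents, assessors or analyst, and the SAP does not either. In section 11 the arms differ in the timing of the repeat dose (12 hours vs 20 minutes) and in maintenance frequency (twice vs once daily). No dummy dosing is described.

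On expectation, section 3 says of phenobarbitone that "its efficacy is limited and it has significant adverse effects", and then "Levetiracetam is emerging as a safer alternative with promising seizure control rates".

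**The concern.** An adverse drug reaction, as the term is normally used, is an adverse event that someone has ascribed to a drug. In a sick neonate the same sign may be put down to the drug or to the underlying illness. If the person deciding knows the arm and expects one drug to be better tolerated, the share of events ascribed to the drug can differ by arm. The chi-square test then compares attribution as well as occurrence.

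The direction of the written expectation favours levetiracetam, so a drift of this kind would tend to support the conclusion the trial hopes to draw. Safety is half of the aim stated in section 3. Events that were never recorded as reactions cannot be recovered by any analysis of the attributed counts.

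A second gap sits beside the first. Use of a further anticonvulsant is itself an outcome, so some neonates are expected to receive one. Nothing says which drug a later reaction is charged to.

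**Working it through.** **What the plan supplies.** It gives no figure for this outcome, so there is none to reproduce. From it I take 50 per arm (Protocol section 8), two-sided α = 0.05 and a chi-square test (SAP). The 50 is used as stated. It does not follow from the section 8 assumptions, since [1.96·√(2·0.6·0.4) + 0.842·√(0.7·0.3 + 0.5·0.5)]² / 0.2² gives about 93 per arm. That is a separate matter, and this point does not rest on it.

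**What is assumed.** The true event rate e is equal in both arms. The attributed share is a_P on phenobarbitone and a_L on levetiracetam. The documents give none of these, so a range is shown.

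**Step 1, recorded rates.** Recorded rate = e × attributed share. For e = 30%, a_P = 60%, a_L = 20%: 0.30 × 0.60 = 18% and 0.30 × 0.20 = 6%.

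**Step 2, chance of a significant result.** For every pair of counts (x_P, x_L) out of n = 50 per arm, compute z = [(x_P − x_L)/n] / √[p̄(1 − p̄)·2/n], with p̄ = (x_P + x_L)/(2n). Sum the two binomial probabilities over all pairs with |z| > 1.96. This is the exact rejection rate of the uncorrected Pearson chi-square. The last column repeats it with the continuity correction.

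| Event rate, both arms | Attributed, phenobarbitone vs levetiracetam | Recorded | Uncorrected | Corrected |
|---|---|---|---|---|
| 30% | all events counted | 30% vs 30% | 5% | 3% |
| 30% | 55% vs 45% | 16.5% vs 13.5% | 8% | 4% |
| 30% | 60% vs 40% | 18% vs 12% | 14% | 8% |
| 30% | 60% vs 20% | 18% vs 6% | 48% | 33% |
| 10% | 60% vs 20% | 6% vs 2% | 14% | 3% |

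**Step 3, hand check of the 18% vs 6% row.** Pooled SE = √(0.12·0.88·2/50) = 0.0650. Unpooled SE = √[(0.18·0.82 + 0.06·0.94)/50] = 0.0639. Φ[(0.12 − 1.96·0.0650)/0.0639] = Φ(−0.12) ≈ 0.45, close to the exact 48%.

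**Step 4, larger samples.** Section 8 also admits every eligible neonate over one year, so the final number is open. At 100 per arm and a 30% event rate, the 60% vs 40% row rises from 14% to 22% and the 60% vs 20% row from 48% to 77% (uncorrected). More patients estimate the same biased difference more precisely.

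**Step 5, effect of dropping attribution.** When all events are counted at a 30% or 40% rate, or attribution is equal at 50% in both arms, the rejection rate is about 5% (0.050 to 0.055 at 50 per arm). This holds only if detection and recording are also equal between arms.

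**The case against.** The strongest reply is that the plan contains no attribution rule. A reader might infer that events enter the count only after the team ascribes them to the drug, but neither document says so. Section 12 has only a label, section 13 refers to side effects, and the proforma might already be a neutral checklist. This stands as a limit: the need for a causal judgement comes from the ordinary meaning of the term, and how it would be made is unknown. It does not remove the point, because the outcome as named still calls for attribution and nothing states how that is protected.

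A reader might also infer that the protocol calls phenobarbitone harmful, or shows its assessors to be biased. It does neither. Its words are "however, its efficacy is limited and it has significant adverse effects. Levetiracetam is emerging as a safer alternative", and an expected advantage is a normal part of a trial rationale. The passage bears only on the likely direction of any drift.

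Third, the size depends on the scenario. The 48% needs a threefold gap in attribution and an uncorrected test. A gap of 55% vs 45% gives 8%, or 4% with the correction. This stands, and no single figure should be quoted as the effect.

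Finally, this is one of five secondary outcomes, and death needs no attribution. That bears on priority. It does not make the count of reactions sound.

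**Conclusion.** The concern holds as a possibility that the plan leaves open. The safety count depends on attribution, and no causality method or masking is stated. The arms can be told apart by their schedules, and the stated expectation points one way. Differential attribution could therefore yield a significant safety difference with equal event rates.

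The documents do not show that this has happened or how large it would be. Under the assumed rates above, with 50 per arm and the uncorrected test, the false-positive rate runs from about 8% to 48%, against a nominal 5%. It is lower with a continuity correction and higher with more patients. The point merits a change because the remedy is cheap, but it concerns a secondary outcome.

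**What to change.** In Protocol section 12 and the SAP, define the safety outcome as the proportion of all randomized neonates with any adverse event from one fixed list, counted from the first dose and analysed by allocated arm. The clinical team should set the list and give each item an objective criterion, using vital signs and laboratory values already recorded where possible. Events are ticked on the existing proforma whatever their presumed cause.

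Make the common 72-hour window the main comparison and also report events through discharge. Section 13 monitors both periods, so stopping at 72 hours would drop events the protocol already plans to watch. Flag whether each event came before or after any second-line drug, as description only, because that split depends on what happened after randomization. Keep attributed reactions as a descriptive table.

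The cost is a tick-list and a few lines of SAP text, with no added tests or staff where the criteria use data already recorded. There are two drawbacks. Illness-related events are counted too, which may dilute a true difference between the drugs. Unmasked staff still record the events, so some detection bias may remain; objective criteria reduce it but do not remove it.
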